## 1. Introduction

This Statistical Analysis Plan (SAP) describes the analyses and data presentations for Oscotec Inc.'s protocol OSCO-P2101 Version 4.0 (Amendment 3, dated 22 Apr 2020) "A Phase 2, Multicenter, Randomized, Double-Blind, Placebo-Controlled, Parallel Dose Study to Evaluate the Efficacy and Safety of Oral SKI-O-703, SYK Inhibitor, in Patients with Persistent and Chronic Immune Thrombocytopenia (ITP)" which was originally issued on 09 Jan 2019. It contains definitions of analysis populations, derived variables and statistical methods for the analysis of efficacy, safety, pharmacokinetics (PK) and pharmacodynamics (PD).

There is one final analysis and one interim analysis planned for this study. This SAP is prepared for final analysis, and interim analysis is planned in a separate interim analysis SAP. Throughout these SAPs, the treatment groups will be referred to as the 200 mg twice daily (BID) group, the 400 mg BID group, and the placebo group. The purpose of the SAP is to ensure the credibility of the study findings by pre-specifying the statistical approaches to any data analysis prior to database lock. This SAP will be finalized and signed prior to the final database lock.

All statistical analyses detailed in this SAP will be conducted using SAS® 9.4 or later (SAS Institute Inc., Cary, North Carolina).

## 2. Objectives

### 2.1. Primary Objective

To evaluate the safety and efficacy on the primary endpoint (platelet response) of select (200 mg BID and 400 mg BID) doses of SKI-O-703 compared to placebo in patients with persistent and chronic ITP, with a platelet count <30,000/ $\mu$ L on 2 occasions at least 7 days apart with the confirmatory count being taken during Screening.

### 2.2. Secondary Objectives

The secondary objectives of this study are as below:

- To evaluate the efficacy on the secondary endpoints of select (200 mg BID and 400 mg BID) doses of SKI-O-703 compared to placebo in patients with persistent and chronic ITP
- To investigate the PK profile of SKI-O-592 (the free base of SKI-O-703) and its metabolites (M2 and M4) in patients with persistent and chronic ITP
- To evaluate the effects of SKI-O-703 on PD biomarkers in patients with persistent and chronic ITP.

### 2.3. Exploratory Objectives

The exploratory objectives of this study are as below:

- To evaluate the PK/PD relationship between plasma concentrations of SKI-O-592, M2, and M4 and the percent change in activated CD63+ basophils in peripheral blood in patients with persistent and chronic ITP
- To evaluate the changes of the exploratory endpoints of select (200 mg BID and 400 mg BID) doses of SKI-O-703 compared to placebo.

[figure not shown]
### **3. Investigational Plan**

#### **3.1. Overall Study Design and Plan**

This is a randomized, double-blind, multicenter, placebo-controlled, parallel dose study to evaluate the efficacy, safety, tolerability, PK, and PD of select (200 mg BID and 400 mg BID) doses of SKI-O-703 in persistent and chronic ITP patients who have failed to respond or relapsed after prior therapy, with a platelet count  $<30,000/\mu\text{L}$  on 2 occasions at least 7 days apart with the confirmatory count being taken during Screening (the most recent result from the central laboratory will be considered as the confirmatory platelet count, when an unscheduled visit(s) is performed during the screening period).

A minimum of 60 patients are planned to enrol in 3 treatment groups (24 patients in each of the active treatment groups and 12 patients in the placebo group). Patients will be randomly assigned to the 3 groups using a 1:2:1 ratio to receive one of the 2 select doses of SKI-O-703 or placebo. First 5 patients randomly assigned in the study will have the safety run-in period for the first 1 week with interim safety and PK assessments on Day 8 ( $\pm 2$  days). Patients in the safety run-in period will continue to be dosed whilst the interim analysis is being conducted. However, further enrollment in each treatment group will only resume after safety and PK data of the first week for the first 5 patients are reviewed and considered satisfactory by the Data Monitoring Committee (DMC). A subset of at least 20 patients, who are not included in the safety run-in period, will be randomized to undergo PK/PD assessments at a selected number of sites. Randomization will be stratified to balance patients with respect to prior TPO-receptor agonist use (yes/no) and degree of baseline thrombocytopenia (ie, baseline platelet count  $<$  or  $\geq 15,000/\mu\text{L}$ ). A schematic diagram of the overall study design is presented in [Figure 3-1](#) and [Figure 3-2](#).

[figure not shown]
**Figure 3-1 Study Design Schematic (for the First 5 Patients in the Safety Run-in Period only)**

Abbreviation: BID, twice daily

Note: First 5 patients randomly assigned in the study will have safety run-in period for the first 1 week with interim safety and PK assessments on Day 8 ( $\pm 2$  days). Patients in the safety run-in period will continue to be dosed whilst the interim analysis is being conducted. However, further enrollment in each treatment group will only resume after safety and PK data of the first week for the first 5 patients are reviewed and considered satisfactory by the Data Monitoring Committee.

**Figure 3-2 Study Design Schematic (For Patients Other Than Enrolled in the Safety Run-in Period)**

Abbreviation: BID, twice daily

### **Screening Period**

The study will include up to 4 weeks of screening period. All potential patients will sign and date the informed consent form (ICF) prior to any study assessments or procedures. These patients will be assessed as per the eligibility criteria at Screening. After completing all screening assessments, patients who meet all the inclusion and none of the exclusion criteria will proceed to the treatment period.

### **12-week Treatment Period**

- *1-week Safety Run-in Period (for the first 5 patients only):* First 5 patients randomly assigned in the study will have the safety run-in period for the first 1 week with interim safety and PK assessments on Day 8 ( $\pm 2$  days). Patients in the safety run-in period will continue to be dosed whilst the interim analysis is being conducted. However, further enrollment in each treatment group will only resume after safety and PK data of the first week for the first 5 patients are reviewed and considered satisfactory by the DMC.

For all patients, on Day 1, patient's eligibility will be confirmed and baseline safety evaluations will be performed (ECG, physical examination, vital sign measurements, and

safety laboratory assessment). Eligible patients will be randomly assigned to receive either one of the doses of SKI-O-703 or placebo. On Day 1, the investigative site staff will administer the morning dose. The evening dose of study medication will be administered 12 hours after the morning dose. Patients will be administered the study medication with enough water to swallow the capsule.

After dosing, all patients will be subjected to safety assessments and a subset of at least 20 patients, who are not included in the safety run-in period, will be subjected to PK and PD assessments according to the Schedule of Events ([Appendix 15.1](#)). Patients enrolled in the safety run-in period will be admitted for 24 hours on Days 1, 8, and 84 of the study. Patients selected for the PK/PD portion of the study will be admitted for 24 hours on Days 1 and 84 of the study.

The maximum duration of study participation for a patient will be 20 weeks, which consists of up to 4 weeks of screening period, 12 weeks of treatment period, and 4 weeks of follow-up period.

## 3.2. Study Endpoints

### 3.2.1. Primary Endpoint

The primary endpoint, patient platelet response, is defined as platelet count  $\geq 30,000/\mu\text{L}$  and doubling the baseline (average of 2 previous counts), at any visit during the treatment period and without the use of rescue medication. Refer baseline definition to Section 4.2.

### 3.2.2. Secondary Endpoints

#### 3.2.2.1. Patients Achieving Two or More Pre-specified Platelet Counts

- Patients able to achieve 2 or more consecutive platelet counts of  $\geq 30,000/\mu\text{L}$  separated by at least 5 days and without use of rescue medication
- Patients able to achieve 2 or more consecutive platelet counts of  $\geq 30,000/\mu\text{L}$  with an increase of platelet count of  $\geq 20,000/\mu\text{L}$  from baseline separated by at least 5 days and without use of rescue medication
- Patients able to achieve 2 or more consecutive platelet counts of  $\geq 50,000/\mu\text{L}$  separated by at least 5 days and without use of rescue medication
- Patients able to achieve 2 or more consecutive platelet counts of  $\geq 100,000/\mu\text{L}$  during the treatment period, separated by at least 5 days and without use of rescue medication
- Patients able to achieve platelet counts of  $\geq 50,000/\mu\text{L}$  at 3 of the last 4 visits.

#### 3.2.2.2. Change from Baseline in Platelet Counts

- Change from baseline in the average of the last 2 platelet counts during the treatment period.

For each patient, the change from baseline in the mean of the last 2 platelet counts during the treatment period will be calculated. For those patients with only 1 platelet count during treatment period, the change from baseline in the single platelet count will be used.

#### *3.2.2.3. Time to First Platelet Response*

- Time to first platelet response ( $>30,000/\mu\text{L}$  and  $2 \times \text{baseline}$ )

For each patient, the time of the first platelet response is the first visit during treatment period in which platelet count  $\geq 30,000/\mu\text{L}$  without use of rescue medication.

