7.2.3 Time to First Platelet Response

- Time to first platelet response ($>30,000/\mu\text{L}$ and $2 \times$ baseline)

For each subject, the time of the first platelet response is the first visit during treatment period in which platelet count $\geq 30,000/\mu\text{L}$ without use of rescue medication.

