### 4.2. Baseline Definition and Study Day

For platelet count related endpoints, baseline will be defined as the lowest platelet count within 1 month prior to or on the date that the first dose of study drug (SKI-O-703 or placebo) is taken. Data from Central lab will be used first. Otherwise, baseline will be defined as the last non-missing evaluation prior to or on the date that the first dose of study drug (SKI-O-703 or placebo) is taken.

The study day will be calculated as:

- Study day = assessment date - first dose of study drug (SKI-O-703 or placebo) date + 1, if assessment date is on or after the first dose date.
- Study day = assessment date – first dose of study drug (SKI-O-703 or placebo) date, if assessment date is prior to the first dose date.

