### 8.1. Primary Efficacy Endpoint

The primary efficacy endpoint, patient platelet response, is defined as platelet count  $\geq$  30,000/ $\mu$ L and doubling the baseline (average of 2 previous counts), at any visit during the treatment period and without a use of rescue medication. Refer baseline definition to Section 4.2. The average based on last 2 platelet counts at the time of evaluation.

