#### 8.1.1. Primary Analysis

The platelet responses after using rescue medication during treatment period will be set to missing and will be imputed as the average of the last 2 previous non-missing platelet counts. For example, if platelet count in Week 2 Day 8, Week 3 and Week 5 are 45,000, missing, and 48,000 respectively, the average will be calculated by results from Week 2 Day 8 and Week 5.

The primary efficacy endpoint will be summarized as overall platelet response rate (ORR) with exact unconditional 95% confidence intervals (CI) by treatment group. The ORR difference and exact unconditional 95% CI will be provided between each of active treatment groups and placebo group, and between two active treatment groups. The p-value from Fisher's exact test will be presented.

For patients whose ORR cannot be adequately determined, their ORR will be imputed using a non-responder imputation (NRI) approach.

Summary statistics will be provided on the number (%) of patients achieving platelet response by each treatment and the combined active treatment groups. The differences in the ORR, 95% CI and p-value from a Fisher's exact test will therefore be provided for:

- Each active treatment group (200 mg BID, 400 mg BID) vs. placebo
- Combine active treatment groups vs. placebo
- 200 mg BID vs. 400 mg BID.

A logistic regression model will also be performed on platelet response as dependent variable and treatment group, baseline platelet count and prior TPO-receptor agonist use as covariates. The odds ratio for the treatment effect compared to placebo (together with 95% CI and p-value) will be provided.

Bar plots on difference in proportions of ORR and exact unconditional 95% CI will be provided by treatment group and combined active treatment group.

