### **8.2.3. Time to First Platelet Response**

Time to platelet response based on the non-response imputation defined in [Section 8.1.1](#) will be summarized by treatment group using Kaplan-Meier (K-M) methods with median time to platelet response (including two-sided 95% CI). K-M estimates of platelet response rates at 2-week intervals (e.g., 2-week, 4-week, etc) will be provided with corresponding two-sided 95% CIs by treatment group. The K-M curve for time to platelet response (later visit meet criteria) will be presented graphically and compared against placebo curve using log-rank test.

In addition, a proportional hazard model will be implemented as well with treatment, baseline platelet count, and prior TPO-receptor agonist use. The hazard ratios, 95% CIs and p-values will be provided to compare each active treatment group against placebo.

A listing of time to platelet response will also be provided.

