## 12. Changes in the Planned Analysis

Change from v0.2 (sponsor mail approved version):

- General: for coding dictionary (MEDDRA, WHODrug), add "or later" wording to apply newest version if needed.
- General: applied changes in Protocol Amendment 3.
- Section 4.2: added baseline definition for platelet count related endpoints
- Section 4.6.3:
  - specified the PD that may impact the analysis will be excluded from PP set.
  - fixed typo for incorrected referring link (Section 7.2.2 -> Section 7.4.2)
- Section 7.4.2: change the source of dose taken
- Section 8: specified the priority of using result when multiple
- Section 8.1.1: specified the scenario when there are missing visit result.
- Section 8.1.2:
  - correct the value round
  - specified the scenario that model fail to converge due to more visits then subjects
- Section 8.2.1: specified the scenario when there is missing visit result.
- Section 8.2.2: specified the scenario that model fail to converge due to more visits then subjects or imputed value out of range.
- Section 8.2.3: specified the visit/date used for time to response.
- Section 9.3:
  - corrected used results. Both central and local lab results will be used.
  - removed the clinically significant since it's not applicable for this study.
  - removed the platelet count in choosing records when multiple.
  - removed the redundant description
- Section 9.4: removed the clinically significant since it's not applicable for this study.

Change from v1.0 (sponsor approved version)

- Section 7.4.2: Aligned compliance calculation using Subject Diary as resource

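### Time to first platelet response is dated by a sentence that omits the doubling of baseline, and the 3-of-last-4-visits endpoint has no rescue exclusion and no treatment-period limit

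*SAP*

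**What the plan says.** Protocol 7.2.3 and SAP 3.2.2.3 define time to first response in the same two layers. The bullet is "Time to first platelet response ($>30,000/\mu\text{L}$ and $2 \times$ baseline", with no rescue condition. The sentence beneath it states that "the time of the first platelet response is the first visit during treatment period in which platelet count" is at least 30,000/µL without rescue. It does not mention doubling.

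The primary endpoint in SAP 3.2.1 asks for at least 30,000/µL "and doubling the baseline (average of 2 previous counts), at any visit during the treatment period", again without rescue.

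SAP 8.2.3 does not restate the event criterion. It points to 8.1.1 for the non-response imputation and then says: "The K-M curve for time to platelet response (later visit meet criteria) will be presented graphically". For that section, SAP section 12 records that the authors "specified the visit/date used for time to response".

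Protocol 7.2.1 and SAP 3.2.2.1 list five responder endpoints. The last requires at least 50,000/µL at three of the last four visits. The other four all exclude rescue; this one does not. Only the 100,000/µL bullet is confined to the treatment period. SAP 8.2.1 leaves out visits with a missing result and applies non-responder imputation where status cannot be determined. It says nothing on rescue or on the range of visits. Hematology is scheduled at the Week 16 follow-up visit (Protocol Table 2, SAP Appendix 15.1).

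The bleeding bullet (Protocol 7.2.4, SAP 3.2.2.4) names the treatment period only. Its event rule and Protocol 7.7.4 count treatment or follow-up.

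**The concern.** The dating sentence is what a programmer would code. Coded as it stands, it gives an endpoint called platelet response a weaker event than the platelet response tested as primary. The same patient could then be an event in one table and a non-responder in another, and a patient who meets both criteria could get an earlier date under the sentence.

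In the 3-of-last-4 endpoint, counts raised by rescue can qualify a patient. A Week 16 count taken after treatment has ended can create a success, or undo one achieved on drug. With planned arms of 24, 24 and 12, a few reclassified patients could visibly move a secondary result.

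**Working it through.** **The plan's own figure.** The documents give no figure for these secondary endpoints. The only efficacy figure is the primary power of 82.74% (SAP 4.4; 82.7% in Protocol 7.4), for 24 versus 12 patients and 50% versus 1%, two-sided 5%. Using the pooled normal approximation with continuity correction:

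- pooled rate = (24×0.50 + 12×0.01)/36 = 0.3367
- null SE = √(0.3367×0.6633×(1/24 + 1/12)) = 0.1671
- alternative SE = √(0.25/24 + 0.0099/12) = 0.1060
- correction = 0.5×(1/24 + 1/12) = 0.0625
- power = Φ((0.49 − 0.0625 − 1.96×0.1671)/0.1060) = 82.73%

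The figure is reproduced and does not depend on anything below.

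**Doubling.** On single counts the sentence needs a count of at least 30,000. The primary response needs at least max(30,000, 2×baseline). They disagree for counts from 30,000 up to just below 2×baseline, which is an empty range when baseline is 15,000 or less.

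| Baseline (/µL) | Primary response needs | Event by the sentence only |
|---|---|---|
| 10,000 | 30,000 | none |
| 15,000 | 30,000 | none |
| 16,000 | 32,000 | 30,000–31,999 |
| 20,000 | 40,000 | 30,000–39,999 |
| 25,000 | 50,000 | 30,000–49,999 |
| 29,000 | 58,000 | 30,000–57,999 |

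For baselines of 15,000 or less, the bullet differs from the sentence and from the primary endpoint only at exactly 30,000 (strict versus non-strict inequality).

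**Date.** Take baseline 20,000 and counts of 24,000 (Day 4), 32,000 (Day 8), 36,000 (Week 3) and 42,000 (Week 5). The sentence dates the event at Day 8. The full response on a single count is first met at Week 5, since 42,000 ≥ 40,000. If Week n starts on Day 7(n−1)+1, Week 5 is Day 29, a shift of 29 − 8 = 21 days. SAP 8.2.3 reports Kaplan-Meier estimates every 2 weeks.

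**Later visit.** The SAP does not say later than what. If it meant the second of two consecutive visits, the nominal shift would be 4 days (Day 4 to Day 8), 7 (Day 8 to Week 3), 14 (between the visits from Week 3 to Week 11) or 13 (Week 11 to Day 84).

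**3 of the last 4.** For a completer the window is Weeks 7, 9, 11, 12 if limited to treatment, or Weeks 9, 11, 12, 16 if read literally. The windows share three visits. They disagree only when exactly two of the shared three succeed (3 ways) and Weeks 7 and 16 differ (2 ways): 3×2 = 6 of 2⁵ = 32 patterns, three in each direction. These are counts of patterns, not probabilities.

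- 60,000, 55,000, 52,000, 45,000, 20,000 (Weeks 7, 9, 11, 12, 16): 3 of 4 on treatment, 2 of 4 literally.
- 40,000, 40,000, 55,000, 60,000, 52,000: 2 of 4 on treatment, 3 of 4 literally.

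**The case against.** Platelet response is a defined term that includes doubling, and the bullet directly above the sentence repeats it. The sentence can be read as shorthand for dating an event already defined. As to intent, that is probably right. It does not remove the problem, because the operative text still says something else and SAP 8.2.3 cites 8.1.1 for imputation only.

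Week 16 is labelled follow-up, and the analyses in SAP 8.1.2 and 8.2.2 stop at Week 12, so counting it is the less natural reading. That also stands, but the missing rescue exclusion does not depend on it. The omission could be deliberate; the documents do not say so.

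Four stronger readings are tempting, and the documents do not support them:

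- **That first visit and later visit contradict each other.** If response needed two counts, the first visit at which it is met would be the later of the two. The remark is unclear; a conflict is not shown. That it is a dating rule at all is an inference from SAP section 12.
- **That averaging two on-treatment counts gives yet another date, or affects patients with baselines of 15,000 or less.** SAP 8.1 ("The average based on last 2 platelet counts at the time of evaluation") and the example in 8.1.1 ("the average will be calculated by results from Week 2 Day 8 and Week 5") lend this some support. But Protocol 7.7.3 classes a patient as a responder on one qualifying count, and the ambiguity belongs to the primary endpoint.
- **That the discordance falls within the randomization stratum of 15,000/µL or more.** The documents do not say which count sets the stratum.
- **That a missing visit must count as failure.** SAP 8.2.1 expressly excludes missing visits. With a window of Weeks 7, 9, 11 and 12, counting them as failures would make everyone who stops before Week 11 a failure, since at most two counts remain.

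**Conclusion.** The point holds for two secondary endpoints. The dating sentence, followed literally and on single counts, admits events that the primary endpoint rejects whenever baseline exceeds 15,000/µL. The discordant range widens from 2,000/µL at baseline 16,000 to 28,000/µL at baseline 29,000. The 3-of-last-4 endpoint can be decided by rescue-raised counts and, read literally, by an off-drug count. The later-visit remark needs a definition. The bleeding mismatch is minor.

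The documents give no distribution of baseline or on-treatment counts, so neither the share of patients affected nor the effect on the log-rank or Cox result can be computed. The primary endpoint and its power are unchanged. This should be corrected before database lock, but it does not threaten the trial's main conclusion.

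**What to change.** 1. In SAP 3.2.2.3 and 8.2.3, date the event at the first treatment-period visit at which the full primary response is met: at least 30,000/µL, at least twice baseline, no rescue. Use the primary endpoint's baseline and evaluation rule. Baseline is itself stated two ways, as an average of two counts in SAP 3.2.1 and in SAP 4.2 as "baseline will be defined as the lowest platelet count within 1 month prior to or on the date" of first dose. Settle that for the primary endpoint and carry it over. Define the later-visit remark or reconcile it with the first-visit wording.
2. Give the 3-of-last-4 bullet the rescue exclusion its four siblings carry and a treatment-period limit. Add the same limit to the three siblings that lack it. If either omission was intended, say so.
3. In SAP 8.2.1, state how excluding missing visits applies to the last-4 window, in particular whether an earlier visit moves in. Counting a missing visit as not met is one option, with the consequence for early stoppers noted above; the choice is the sponsor's.
4. Align the bleeding bullet with its event rule and Protocol 7.7.4.

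The cost is wording only, with no new data or visits. Protocol 7.7 leaves data conventions to the SAP, but Protocol 7.2.1 and 7.2.3 print these endpoints themselves. Record the changes in SAP section 12 as clarifications of that text, so that the two documents do not disagree.
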